2.1.2 Secondary Objectives

1. The proportion of patients receiving coronary angiography and revascularisation at index hospitalisation and during 12-month follow up.
2. The proportion of patients representing or readmitted to hospital with suspected ACS/recurrent chest pain up to one year after index presentation.
3. The use of cardiovascular treatment during index hospitalisation and preventative therapies on discharge.
4. Length of stay at index hospitalisation.
5. The use of NHS resource including hospitalisation and other investigations and interventions.
6. The proportion of patients with symptoms, morbidity and mortality up to one year.
7. Quality of life.
8. The incremental cost per QALY gained by providing CTCA compared to current standard practice.

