7. DATA COLLECTION

Data collection for primary, secondary and safety clinical outcomes

Data will be collected by the research team from routinely available NHS hospital records or trial specific documentation and will include the following categories: eligibility criteria, consent and baseline demographics, comorbidities, regular treatment, ECG results, vital signs, blood results, admission and discharge diagnoses, cardiology and other relevant investigations or interventions, length of stay, repeat hospitalisations and adverse events. Detail will also be collected on the trial intervention including timing, details of the procedure including dose, reporting clinician, report including incidental findings, and any adverse events as a result of the intervention.

Collection of cost and health outcome data

Length of stay and major adverse cardiac events will be recorded from telephone contact of patients, hospital and primary care records, and deaths from the Central Registry Office or equivalent. At baseline, 1, 6 and 12 months, quality of life and angina symptoms will be measured using the EQ-5D-5L and ROSE questionnaires by direct patient interview, postal or email survey with telephone follow up for non-responders after two mailings two weeks apart.

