8. STATISTICS AND DATA ANALYSIS

Statistical Analysis

The trial will be reported on an intention-to-treat basis. The primary outcome is defined as first event of all cause death or subsequent non-fatal MI type 1 or 4b. Time to primary outcome is defined as time from randomisation to primary outcome. Patients discontinuing the study (for any reason) prior to reaching primary outcome will have their time to primary outcome censored at the last contact date. The relationship between intervention and the primary outcome will be analysed using Cox proportional hazard regression adjusted for study site (used to stratify the randomisation), baseline GRACE score, and previous CAD. The results will be expressed as a hazard ratio with the corresponding 95% confidence intervals and p-value. The individual elements of the composite primary outcome will be reported separately. Subgroup analysis on the primary outcome is planned for age, sex, baseline GRACE score, previous CAD, baseline ECG result, baseline troponin concentration, and presentation to a study site with or without on-site invasive coronary angiography facilities. These will be assessed by examining the effect of entering the treatment by subgroup interaction into the Cox regression model. Secondary outcomes will be analysed using appropriate methods: logistic regression for binary outcomes and linear regression for normally distributed continuous outcomes, adjusted as described above. Continuous outcomes that are not normally distributed will be analysed using appropriate nonparametric techniques. Every effort will be made to minimise missing data, and our primary analysis will be a complete case analysis. If there is a sufficient level of missing data for it to affect our conclusions, a multiple imputation analysis will be undertaken, using clinically appropriate variables, as a sensitivity analysis. Significance testing will use a hierarchical approach – for the primary outcome and the key secondary outcomes, statistical significance will be declared if the outcome in question, and all prior outcomes listed, have $p < 0.05$. P-values will be reported for all other outcomes but will not be declared to be significant.

A full statistical analysis plan will be written during the trial and finalised prior to database lock.

Economic analysis

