The intention-to-treat (ITT) population will include all patients who have been randomised into the RAPID-CTCA trial, and who did not withdraw consent for any of their data to be stored in the trial database. Patients will be analysed in the group to which they were allocated to, regardless of the

Statistical Analysis Plan	RAPID-CTCA
Version No	2.0
Date Finalised	19 Aug 2020

intervention they actually received. Analyses will be based on the ITT population, unless otherwise specified.

In general terms, categorical data will be presented using counts and percentages, whilst continuous variables will be presented using the mean, median, standard deviation (SD), minimum, maximum, lower and upper quartiles and number of patients with an observation (N). Data will be split by intervention group and time point where applicable.

All applicable statistical tests will be 2-sided and will be performed using a 5% significance level. 95% (2-sided) confidence intervals (CIs) will be presented. All analyses are testing superiority, rather than equivalence or non-inferiority. Significance testing will use a hierarchical approach – for the primary outcome and the key secondary outcomes, statistical significance will be declared if the outcome in question, and all prior outcomes listed, have $p < 0.05$. P-values will be reported for other outcomes but will not be declared to be significant.

Where there is missing data for an outcome variable, in the first instance, those records will be removed from any formal statistical analysis relating to that outcome variable (complete case analysis), unless otherwise specified. In tabulations, numbers of missing observations will be provided, but percentages will not include them.

Distributional assumptions underlying the statistical analyses will be assessed by visual inspection of residual plots. Normality will be examined by normal probability plots. If the distributional assumptions for the parametric approach are not satisfied, further data transformation (to alleviate substantial skewness (i.e. normalizing) or to stabilise the variance), or other suitable methods will be considered. This will be documented in the statistical results report together with the reasoning supporting the action taken, if applicable.

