Table: N (%) of patients with 'No chest pain', 'Non-exertional chest pain', 'Chest pain on exertion' will be presented at month 1, 6, and 12 and summarised by allocated intervention group. No formal statistical testing will be performed.

13. Patient satisfaction at 1 month;

Data to be tabulated, without formal statistical testing.

14. Clinician certainty of presenting diagnosis after CTCA;

Table [continuous]: Present data on change from baseline, in addition to final values.

Note: clinician certainty of presenting diagnosis is on a scale of 0-10 where 0 is least certain and 10 is most certain

15. Quality of Life (measured by EQ-5D-5L up to 12 months).

NB Analysis of this outcome will be done by the health economics team, not the statistical team, and details are in the Health Economic Analysis Plan.

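### SAP 4.6 item 12 tabulates chest pain by arm with no between-arm estimate, contrary to protocol section 8 and SAP section 3, and gives baseline ROSE no use

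*SAP*

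**What the plan says.** SAP 4.6 item 12 sorts patients into no chest pain, non-exertional pain and pain on exertion. Counts and percentages in these categories "will be presented at month 1, 6, and 12 and summarised by allocated intervention group. No formal statistical testing will be performed". Nothing else is specified for this outcome.

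Three other places bear on it:

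- Protocol section 8, reproduced in SAP section 2: "Secondary outcomes will be analysed using appropriate methods: logistic regression for binary outcomes and linear regression for normally distributed continuous outcomes, adjusted as described above". On outcomes outside the testing hierarchy it adds: "P-values will be reported for all other outcomes but will not be declared to be significant".
- SAP section 3 (Overall Statistical Principles): "P-values will be reported for other outcomes but will not be declared to be significant". The same section says that two-sided 95% intervals will be presented.
- Protocol section 7: at baseline and at 1, 6 and 12 months, "quality of life and angina symptoms will be measured using the EQ-5D-5L and ROSE questionnaires".

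Chest pain is among the Other Endpoints in protocol section 2.2.2, so it is not a key secondary. The related aim is secondary objective 6 in protocol section 2.1.2: "The proportion of patients with symptoms, morbidity and mortality up to one year".

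**The concern.** Patient-reported chest pain is the symptom outcome of a trial whose patients all entered with symptoms. The protocol leads a reader to expect an analysed comparison, but the SAP supplies three tables of percentages.

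Without an interval, a chance difference between arms can be read as an effect of CTCA, and a real difference is left unquantified. Responder mix adds to this. Follow-up symptoms come by interview, post or email, with telephone chasing of non-responders, and SAP section 3 excludes missing observations from percentages. The baseline ROSE category would help show whether responders in the two arms started alike. Item 12 begins at month 1, however, and the SAP 4.2 baseline table lists descriptors of the presenting pain but not ROSE.

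**Working it through.** **1. The passages side by side**

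| Question | Protocol section 8 | SAP section 3 | SAP 4.6 item 12 |
|---|---|---|---|
| Is the outcome analysed by arm? | Yes, by appropriate methods | Analyses generally adjusted unless otherwise specified | Tabulated only |
| Covariates | Site, GRACE, previous CAD | Same three | None |
| 95% interval | Specified for the primary hazard ratio | Yes | None |
| P-value | Reported for all other outcomes | Reported for other outcomes | None |

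The neighbouring items differ from item 12. Items 1 to 7 and 11 get adjusted and unadjusted hazard ratios with intervals. Items 8 and 9 get adjusted and unadjusted odds ratios with intervals. Item 10 gets a Hodges-Lehmann shift with an interval. Items 13 and 14 are tabulated only, and item 15 is passed to the Health Economic Analysis Plan.

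**2. The plan's own figure**

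The point rests on no stated figure, but the sample size fixes the arm size. Read 6.8% as the overall rate with a 3.4-point difference, that is 8.5% v 5.1%. For 80% power and two-sided 5%, the pooled-variance formula is:

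n per arm = [1.96 × √(2 × 0.068 × 0.932) + 0.842 × √(0.085 × 0.915 + 0.051 × 0.949)]² / 0.034²

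= (0.698 + 0.299)² / 0.001156 ≈ 860

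The total is 2 × 860 = 1720, as stated.

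**3. Could the data support an estimate?**

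Inputs: 1735 patients randomised 1:1, from the protocol. Assumed, because the documents give neither: questionnaire return of 60–80%, and prevalence of the chest pain category of 25–45% in both arms.

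- Responders per arm: 1735/2 × 0.6 to 0.8 = 520 to 694.
- Odds ratio: the 95% limits are the estimate multiplied and divided by exp(1.96 × √(2/(n p(1−p)))). With n = 520, p = 0.25 this is exp(0.281) = 1.32. With n = 694, p = 0.45 it is exp(0.212) = 1.24.
- Risk difference: half-width = 1.96 × √(2p(1−p)/n). With n = 694, p = 0.25 this is 4.6 points. With n = 520, p = 0.45 it is 6.0 points.
- Difference detectable with 80% power: 2.80 × √(2p(1−p)/n) = 6.5 to 8.6 points at the same two corners.

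Wider assumptions do not change the picture. With 860 per arm and prevalence of 10–50%, the half-width is 2.8 to 4.7 points at full response and 3.7 to 6.1 points at 60% response (516 per arm).

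These figures ignore covariate adjustment. They show only that a useful estimate is feasible.

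**4. What the planned table does yield**

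Counts and denominators by arm allow a crude difference p₁ − p₂ with standard error √(p₁(1−p₁)/n₁ + p₂(1−p₂)/n₂). They do not allow adjustment for site, GRACE score, previous CAD or baseline symptoms.

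**The case against.** A fair defence has several parts.

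- **The objective is worded as a proportion, and the table supplies it.** This stands. A reader might infer that the symptom objective cannot be answered, but the documents do not support that. Proportions by arm are given at three time points and a crude comparison can be derived. Item 11, re-presentation with suspected ACS or recurrent chest pain, also gets hazard ratios, although it measures hospital contact and not symptoms.
- **Section 8 does not ask for baseline ROSE.** This stands. It might be inferred that leaving ROSE out breaches section 8, but the covariates named there are site, GRACE and previous CAD. The omission is a gap between what protocol section 7 collects and what the SAP analyses.
- **Section 8 names no model for three categories.** This stands. Logistic regression is tied to binary outcomes and linear regression to normally distributed ones, so only the general requirement of an appropriate adjusted method applies. SAP section 3 also qualifies its adjustment rule with an exception clause. The p-value sentence carries no such exception in either document, so that conflict is firm.
- **Missing questionnaires will be visible.** This stands in part. SAP section 3 requires numbers missing to be tabulated. Item 12 does not say whether deaths are counted among them, and numbers missing do not show whether responders were alike at baseline.
- **Self-report in an open trial is better left descriptive.** This stands in part. An interval does not capture reporting bias, and adjustment for baseline ROSE does not in general remove non-response bias. But percentages by arm carry the same biases, and hide the sampling error as well.
- **Descriptive reporting is not peculiar to chest pain.** True of items 13 and 14. That does not explain the departure for item 12.

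**Conclusion.** The point holds as an unexplained departure with limited consequences. Item 12 specifies no between-arm estimate, interval or p-value. Protocol section 8 calls for analysis and for p-values on all other outcomes, SAP section 3 repeats the p-value rule, and items 1 to 11 are all given estimates. Separately, baseline ROSE is collected without a stated use.

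The loss is a pre-specified, adjusted comparison of symptoms with its uncertainty. With the assumed return and prevalence, that comparison would have had an odds-ratio interval of the estimate times or divided by about 1.24 to 1.32. Those assumptions bear on feasibility only; the textual conflict does not depend on them. Chest pain lies outside the testing hierarchy, so no primary result, key secondary result or error rate changes. The documents do not say how well baseline ROSE predicts later pain, so no gain in precision is claimed for adjusting on it.

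**What to change.** In SAP 4.6 item 12, keep the three-category table and add, at months 1, 6 and 12, an odds ratio with 95% interval and p-value from logistic regression. The outcome should be any chest pain or exertional chest pain, with the choice stated in advance; a binary outcome avoids assuming that the three categories are ordered. Adjust for site, GRACE score and previous CAD as set out in SAP section 3, plus baseline ROSE category. Label the p-values descriptive, as SAP 4.6 already does.

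Add baseline ROSE category by arm to SAP 4.2, and show deaths separately from non-response in item 12. If the sponsor prefers to keep the table alone, the SAP should say why it departs from protocol section 8.

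The cost is SAP wording and three models on data already collected (six if both outcomes are modelled). The testing hierarchy is untouched. The estimate would still come from responders only and from self-report in an open trial, and should be described that way.

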4.7 Safety

1. Summary table of adverse events, by treatment group and overall. Number of events and number of patients who had an event, showing all adverse events, serious adverse events, and non-serious adverse events. Table to include related/not related, and any categorisation provided by the Chief Investigator.
2. Radiation exposure from CTCA in patients allocated CTCA, who received CTCA as the trial intervention. Number of patients in this category, plus summary of the effective radiation dose for this group of patients. A dose length product to mSv conversion factor of 0.014 mSv/mGy/cm will be used. Number of patients who had radiation exposure that met the criteria for deviation, split by whether patient had (deviation=dose-length product>686 mGy.cm) or did not have (deviation=dose-length product >1500 mGy.cm) typical characteristics (typical = heart rate during scan <70 beats per minute, heart in sinus rhythm, and BMI <25 kg/m²)
3. Other cardiac and non-cardiac findings in patients allocated CTCA, who received CTCA as the trial intervention (categorical).

4.8 Other analyses

Cost effectiveness analysis is specified in the Health Economics Analysis Plan

Clinical investigations during trial (these may be re-categorised after taking in to account the text from the 'other relevant' category):

- Echo (Yes/No)
- Radionuclide scan (Yes/No)
- 24 hour tape (Yes/No)
- Abdominal ultrasound (Yes/No)
- Upper gastrointestinal endoscopy (Yes/No)
- Exercise test (Yes/No)
- MRI angiography (Yes/No)
- Stress echo (Yes/No)
- Result of final ECG
- Rhythm of final ECG
- Abnormal final troponin (Yes/No)
- Other relevant, as specified on categorisation of 'other investigations' by Chief Investigator

Clinical process:

- Most applicable disposition place (place sent after initial attendance location)
- Most applicable discharge diagnosis

5. Validation and QC

The following will be done by a second statistician:

1. Separate programming and checking of primary outcome results and conclusions.
2. The statistical report will be read and sense-checked.

6. Data sharing

A file, or set of files, containing the final analysis data will be prepared as part of the final analysis. Within the University of Edinburgh environment, under certain safeguards, these de-identified datasets can be shared. If a fully anonymised version is required for external sharing, further discussion is needed.

7. References

1. SAS® Institute Inc. SAS for Windows. SAS Institute Inc.: Cary, NC, U.S.A
2. Fox et al for the GRACE Investigators. Prediction of risk of death and myocardial infarction in the six months after presentation with acute coronary syndrome: prospective multinational observational study (GRACE). *BMJ* 2006; 33:1091-1094.

RAPID-CTCA_SAP v2.0

Final Audit Report

2020-08-26

Created:	2020-08-19
By:	[name] ([contact])
Status:	Signed
Transaction ID:	CBJCHBCAABAAM8vR534O7SLn6kZJDglwhbxvkB7mTVti

"RAPID-CTCA_SAP v2.0" History

 Document created by [name] ([contact])

2020-08-19 - 14:43:43 GMT- IP address: [name]

 Document emailed to [name] ([contact]) for signature

2020-08-19 - 14:57:28 GMT

 Email viewed by [name] ([contact])

2020-08-19 - 14:57:58 GMT- IP address: [name]

 Document e-signed by [name] ([contact])

Signature Date: 2020-08-19 - 14:58:39 GMT - Time Source: server- IP address: [name]

